Postoperative monitoring, diagnostic and lab tests will be done according to Spectrum Health standard of care. Current standard of care for the postoperative cardiac surgery patient at this institution consists of continuous telemetry monitoring, collection of arterial blood gases, complete blood count, basic metabolic panel and blood glucose at regular intervals. An EKG is obtained on arrival to the recovery area and any time a cardiac dysrhythmia is noted.

In addition to standard of care, subjects who were randomized to the treatment arm of the study will have a pre-discharge transthoracic echocardiogram to assess the absence or presence of thrombus in the left atrium. If thrombi are noted, subjects will be anticoagulated per standard of care.

The highest risk of POAF is within the first 48 to 96 hours after surgery. All post-operative patients are on continuous 24 hour telemetry after surgery until hospital discharge. While it depends on the index procedure that was done, the usual length of stay at this institution following elective cardiac surgery is 5 to 7 days.

If subjects develop POAF, paroxysmal or sustained, they will be treated with standard medications and protocols already in place for this complication.

The current protocol to treat POAF first entails escalation of beta blocker therapy if it is tolerated. If further treatment is necessary, patients are loaded with a dose of IV amiodarone and then changed to oral amiodarone for four weeks or longer if appropriate.

Our current standard of care at Spectrum Health for POAF anticoagulation is as follows. For POAF that persists for more than 24 hours or is episodic and occurs more than once, anticoagulation is initiated. Warfarin or one of the new oral anticoagulants such as dabigatran, rivaroxaban or apixiban will be used tailored to the individual patient utilizing their CHA2DS2-VASc score and surgeon preference.

In addition, all patients who receive a mechanical valve or a bio prosthetic mitral valve are started on an anticoagulant on postoperative day 2. The dose is titrated to an INR of 2.5-3.5.

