To our knowledge isolated radiofrequency epicardial pulmonary vein lesions have not resulted in endocardial thrombus. Nor has this been reported with the AtriCure clamp. The current recommendations are to anticoagulate patients who undergo surgical ablation with endocardial lesions or full surgical Maze procedures which involve additional lesions in the left and/or right atrium (35,36). At Spectrum Health we perform 1200 open heart surgery procedures per year and it is not our standard to anticoagulate patients after isolated PVI who remain in sinus rhythm except for a daily aspirin. Of note all cardiac surgical patients are on daily Lovenox postoperatively to prevent deep venous thrombosis.

Subjects will be visited daily by research staff during the index hospitalization. The EMR will be reviewed with a focus on any episodes of POAF or any other cardiac dysrhythmias, any need for pacemaker, chest tube drainage or need for blood transfusion beyond what is normal for this patient population.

The initial follow-up for POAF occurrence will be 30 +/-7 days post hospital discharge; this is standard for post-operative surgical care. Additional follow-up, consisting of electronic medical record (EMR) review anywhere care is given, will occur at 6 weeks, 6 months and 12 months post procedure. Review of subject data will include any adverse events that may have occurred, EKG, and echocardiogram review. If data is not available in the EMR, phone calls will be made to subjects.

Data management

Research Electronic Data Capture (REDCap) will be used for randomization and data collection. REDCap is password protected and only IRB study approved personnel will have access to the data.

Standard practice is to enter this group of surgical patient's information into the Society of Thoracic Surgeons (STS) Registry. Subjects in this study will be included in the STS Registry.

Data to be collected will include:

- Subject name, date of birth and medical record number
- Gender, age
- Inclusion/Exclusion criteria
- Medical History: hypertension (HTN), diabetes mellitus (DM), hypercholesterolemia, chronic lung disease, peripheral vascular disease (PVD), coronary artery disease (CAD), CHF, chronic kidney disease (CKD), cerebrovascular disease (stroke/TIA)
- Echocardiogram (pre-op and pre-discharge (treatment arm only)): EF, LA measurement, LV measurement, mitral regurgitation, tricuspid regurgitation

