- Medications, pre- and post-op including name of medication, indication, dose.
- Procedure and date- including number of grafts and type of valve implanted
- CPB time, X-clamp time
- EKG rhythm(s), pre- and post-op (atrial flutter, SVT, VT, etc.)
- Post procedural stroke/TIA
- Post procedural MI
- Post procedural pacemaker implant
- Any bleeding complication
- Any incidents of POAF (date occurred, treatment used,)
- Length of stay

Data will also be collected at 6 weeks, 6 months and 12 months post-procedure. This will include:

- All adverse events
- Any rehospitalizations
- Medications, current and new
- Any episodes of AF or other cardiac arrhythmias
- EKG
- Need for pacemaker

• Echocardiogram: EF, valve gradients, left and right atrial function, pulmonary vein stenosis or presence of suspected thrombus.

In the event that we are unable to find subject information in the EMR at appointed study intervals, we may telephone subjects to inquire how they are and whether or not they have had any adverse events.

Assessments/procedures	Baseline	Hospitalization	Predischarge	Follow up	Follow up	Follow up
	Screening			6 weeks	6 months	12 months
				post	post	post
				procedure	procedure	procedure
				+/-7 days	+/- 7 days	+/- 7 days
Consent	Х					
History/Inclusion and	Х					
Exclusion						
Medication Review	Х	X		X	X	X
Randomization	Х					
AF occurrence and		X		X	X	X
treatment						
Transthoracic echo			X			
			Treatment			
			arm only			
Rehospitalizations				X	X	X
Adverse Events		X		X	X	Х

Adverse events

An adverse event (AE) is any untoward medical occurrence (signs, symptoms, abnormal laboratory findings) in a subject. It does not necessarily have to be caused by the device or procedure to be considered an adverse event.

A serious adverse event is one that led to death, serious deterioration in the health of the subject, resulted in a new hospitalization or prolonging the index hospitalization, a permanent impairment of a body structure or function, or required medical and/or surgical intervention to prevent further lifethreatening illness or injury

A device related adverse event is an event that in the investigators judgement may be related to the investigational device.

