Adverse events reporting will include the categories of cardiac, respiratory, vascular, bleeding, neurological (stroke/TIA), other organ complications and infection. Adverse events will be monitored by research staff and the investigator from the time of cardiac surgery until 365 days post procedure. AEs will be categorized according to seriousness and device and/or procedure relatedness. The monitoring of adverse events will occur from the time of cardiac surgery, throughout the hospitalization, at the 30 day, 6 week +/- 7 days, 6 months +/- 7 days and 12 months +/- 7 days post procedure assessments.

Serious adverse events or serious adverse device-related events will be reported to the FDA and Spectrum Health IRB per the regulations and reporting procedures.

If any thromboembolic events are observed during the study, an adverse event form will be submitted to the FDA. This report will include anonymized information on the procedure, type, and severity of thromboembolic event, the patient specific anticoagulation protocol, and the total number of subjects enrolled and treated in each arm by the event time.

Adverse events will be reported and recorded in REDCap and will include the following information:

- Date of onset first observation
- Description of event
- Seriousness of event
- Causal relationship to device/procedure
- Treatment required
- Outcome/resolution

The investigator and the non-study cardiothoracic surgeon will review all AEs.

For the purposes of this study certain events will be considered part of the expected post-operative course and will not be reported unless the investigator feels they deviate from the norm:

- Post-operative pain requiring medication
- Temporary mental status changes (except TIA/stroke)
- Mild GI disturbances, i.e. decreased appetite, nausea, vomiting, constipation or diarrhea
- Respiratory findings post-surgery, including oxygen usage, pleural effusion, atelectasis
- Minor laboratory findings, including hypokalemia, hyperkalemia, hypocalcemia, hypomagnesemia, leukocytosis, thrombocytopenia, hyperglycemia
- Post-operative anemia d/t intraoperative blood loss/dilution requiring ≤ 2 U transfusion
- Low-grade fever < 38.5∘ C
- Hypo/hypertension requiring treatment
- Mild creatinine increase, ≤ 0.3 mg/dL

Provisions to Monitor the Data for the Safety of Subjects

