Data will be reviewed by a non-study cardiothoracic surgeon; [name]. The review will include subject eligibility, documentation of the consent process, adverse events, and subject withdrawals. Review will occur after every 5 patients have a completed surgical procedure and are discharged from the hospital. Adverse Events (AE) will be evaluated for seriousness, unanticipated, procedural and/or device-relatedness. If any Serious Adverse Events (SAE) occur beyond what is expected in this patient population and are thought to be related to the limited left sided surgical maze procedure, the FDA and Spectrum Health IRB will be notified per reporting practices and the study may be terminated.

Monitoring of patient data will continue throughout the study at the scheduled assessment times.

Withdrawal of subjects

We do not foresee any circumstances in which subjects would want to withdraw from the study. However, subjects may withdraw from this study at any point, it will not be held against them nor involve penalty or loss of benefits to which subjects are otherwise entitled.

Risks/Benefits to Subjects

Neither LAA amputation or pulmonary vein isolation ablation, the 2 components of the limited left sided surgical maze procedure, have been shown to pose additional risk to the subject over the primary open heart procedure (7,8,16,28).

Potential adverse events with this combined procedure are similar to the risks of cardiac surgery and are listed below as described in the AtriCure® Synergy Ablation System Instructions for Use:

- Death
- Excessive bleeding that may require re-intervention
- Cardiac tamponade
- Pulmonary vein stenosis
- Restrictive or constrictive pericarditis
- Infection that may result in sepsis or endocarditis
- Myocardial infarction (MI)
- Stroke or transient ischemic attack (TIA)
- Thromboembolism
- Diaphragmatic (phrenic nerve) paralysis
- Esophageal-left atrial fistula or esophageal rupture
- Atrial perforation or rupture
- Ventricular perforation or rupture
- Atelectasis
- Pneumonia
- Congestive heart failure
- Cardiac valve injury
- Persistent pneumothorax
- Excessive pain and discomfort
- Deep sternal wound infection (mediastinitis)
- Perioperative atrial or ventricular rhythm/conduction disturbance
- Pericardial effusion
- Injury to the great vessels
- Injury to unintended surrounding tissues, including tears and punctures
- Extension of cardiopulmonary bypass time or aortic cross clamp time

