Application will be made to CMS for reimbursement consideration. Subject's health insurance will be billed for costs that are part of usual medical care. Any co-payment, co-insurance or deductible, will be the responsibility of the subject. There are no extra costs to subjects for participating in this research study. The pre-discharge transthoracic echocardiogram required for the study (treatment arm only) will not be billed to the subject or their insurance.

Consent Process

Once a subject has been identified as meeting criteria for the study, the PI and/or other delegated study personnel will explain the study in detail to the subject. This discussion will take place in privacy at Spectrum Health. Adequate time will be allowed for questions. A copy of the consent will be given to the subject to read and review. After allowing the subject adequate time to review the consent, the research coordinator will answer any additional questions and ensure that the subject realizes participation is voluntary. A signed copy of the informed consent will be given to the subject.

Sharing of Results with Subjects

There are no plans to share research results with subjects.

References

- 3. Atrial Fibrillation After Cardiac Surgery ed. Jonathan Steinburg 2007 Springer Science & Business Media

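### Only the maze arm has a study-mandated pre-discharge echocardiogram, so silent cardiac findings are sought in one arm and descriptive adverse event counts by arm are tilted against the maze

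*Combined protocol and SAP*

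**What the plan says.** **The scan.** Procedures Involved in the Research states that, on top of standard care, the following applies: "subjects who were randomized to the treatment arm of the study will have a pre-discharge transthoracic echocardiogram to assess the absence or presence of thrombus" (left atrial). The restriction to one arm is repeated in the Data management list ("Echocardiogram (pre-op and pre-discharge (treatment arm only)): EF, LA measurement, LV measurement, mitral regurgitation, tricuspid regurgitation"), in the schedule of assessments, and under Cost to Subjects ("The pre-discharge transthoracic echocardiogram required for the study (treatment arm only) will not be billed to the subject or their insurance").

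**What controls get.** Standard postoperative care "consists of continuous telemetry monitoring, collection of arterial blood gases, complete blood count, basic metabolic panel and blood glucose at regular intervals", plus an EKG on arrival in recovery and whenever a dysrhythmia is noted. No echocardiogram is listed. For the later visits: "Additional follow-up, consisting of electronic medical record (EMR) review anywhere care is given, will occur at 6 weeks, 6 months and 12 months post procedure". Echo results are abstracted then if they exist, but the schedule places no scan at those times.

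**What counts as an AE.** The Adverse events section reads: "An adverse event (AE) is any untoward medical occurrence (signs, symptoms, abnormal laboratory findings) in a subject". Causation by the device or procedure is not required, and cardiac events are a reporting category. A list of expected postoperative events is exempt from reporting. It includes pleural effusion but not pericardial effusion or atrial thrombus. Pericardial effusion and thromboembolism both appear among the potential adverse events under Risks/Benefits to Subjects. The items recorded for each AE are onset date, description, seriousness, causality, treatment and outcome; how the event came to light is not among them.

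**How the events are used.** A non-study surgeon reviews the data after every five operated and discharged patients. The escalation rule begins "If any Serious Adverse Events (SAE) occur beyond what is expected in this patient population and are thought to be related to the limited left" and goes on to name the maze procedure; the FDA and IRB are then notified and the study may be stopped. FDA reports of thromboembolic events include "the total number of subjects enrolled and treated in each arm by the event time".

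**Formal analysis.** The Safety endpoints section lists death, TIA/stroke, procedure-related bleeding, AF, permanent pacemaker and pulmonary vein stenosis. Statistical Methods names tests for POAF and for secondary outcomes, and none for AEs.

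**The concern.** Contacts and AE windows are otherwise the same in both arms. The one difference is a scheduled look inside the heart in maze patients only. An atrial thrombus, a pericardial effusion, a fall in ejection fraction or new regurgitation without symptoms can be seen and recorded in a maze patient. In a control it surfaces only if something clinical prompts imaging. If the finding prolongs the stay, or needs intervention to avert a life-threatening problem, it also meets the SAE definition.

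Safety is half of the stated objective. With two arms of 30, a handful of events shapes the impression of harm. If the true rates are equal, a table of cardiac AEs by arm would still be expected to show more in the maze arm, and a reader would naturally attribute the excess to the procedure. The per-arm denominators in the FDA report invite the same comparison. An event found by a scan that exists because of the maze may also be judged maze-related more readily.

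**Working it through.** The plan has no figure to reproduce: Sample Size Determination says no calculation was done, and no rate of silent echo findings is given.

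**Inputs from the documents.** n = 30 per arm (Sample Size Determination); significance level 0.10, sidedness not stated and taken as two-sided (Statistical Methods); a scheduled scan in the maze arm only.

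**Assumed inputs.** True rate p of silent, reportable findings, equal in both arms: 5%, 10% or 20%. Probability of detection: d_M in the maze arm, d_C in control.

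**Formulas.** Expected detected events are 30·p·d_M and 30·p·d_C. Counts are independent binomials. The chance of at least one scan-only event in the maze arm with full detection is 1 − (1 − p)^30.

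- p = 5%: 30 × 0.05 = 1.5 expected; 1 − 0.95^30 = 0.785
- p = 10%: 30 × 0.10 = 3 expected; 1 − 0.90^30 = 0.958
- p = 20%: 30 × 0.20 = 6 expected; 1 − 0.80^30 = 0.999

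| Detection, maze / control | p | Expected, maze vs control | Chance maze count is higher | Chance Fisher p < 0.10, maze worse |
|---|---|---|---|---|
| 100% / 0% | 5% | 1.5 vs 0 | 79% | 1.6% |
| | 10% | 3 vs 0 | 96% | 17.5% |
| | 20% | 6 vs 0 | >99% | 74.5% |
| 80% / 10% | 5% | 1.2 vs 0.15 | 65% | 0.5% |
| | 10% | 2.4 vs 0.3 | 85% | 6.7% |
| | 20% | 4.8 vs 0.6 | 97% | 36.7% |
| 50% / 10% | 5% | 0.75 vs 0.15 | 48% | 0.1% |
| | 10% | 1.5 vs 0.3 | 69% | 1.2% |
| | 20% | 3.0 vs 0.6 | 86% | 10.5% |
| 80% / 80% (reference) | 5% | 1.2 vs 1.2 | 36% | 0.2% |
| | 10% | 2.4 vs 2.4 | 40% | 0.9% |
| | 20% | 4.8 vs 4.8 | 43% | 2.0% |

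The last column shows scale only, since the plan names no such test. For orientation, 4 vs 0 of 30 gives a two-sided Fisher p of 0.112 and 5 vs 0 gives 0.052.

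**At one safety review.** Five patients include on average 2.5 maze patients. With full detection that is 2.5 × 0.05 = 0.125 to 2.5 × 0.20 = 0.5 expected scan-only events per review.

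**Direction.** The bias in the difference (maze minus control) equals events missed in control minus events missed in the maze arm: 30·[p_C(1 − d_C) − p_M(1 − d_M)]. With equal true rates and better detection in the maze arm it is always positive, that is, against the maze. It stays positive as long as p_M/p_C is below (1 − d_C)/(1 − d_M), which is 0.9/0.2 = 4.5 at 80%/10% detection and 0.9/0.5 = 1.8 at 50%/10%.

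**The case against.** The strongest reply is that targeted imaging for a procedure-specific risk is reasonable in a 60-patient unblinded feasibility study, and that little in the formal analysis depends on it. Much of this stands.

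- **Safety endpoint.** A reader might infer that it is biased too. The documents do not support that directly: neither thrombus nor effusion is a component. Its one imaging-based component, pulmonary vein stenosis, is not among the fields recorded from the pre-discharge scan. Anticoagulation following a scan-found thrombus could move stroke or bleeding, but in either direction.
- **Error rates.** A reader might quote an inflated false-positive rate for the safety analysis. No between-arm AE test is planned, and the high figures need both a high assumed rate and near-complete one-sided detection.
- **Equal thrombus rates.** The Background places 90% of AF thrombi in the appendage, which is removed only in the maze arm, and the protocol reports no known endocardial thrombus from epicardial pulmonary vein lesions. Equality is therefore only a null scenario. A lower true rate in the maze arm would not remove the bias, because more would then be missed in control.
- **Scope of the scan.** Its stated purpose is thrombus, and effusion is not a listed field. However, ejection fraction and regurgitation are recorded, and an effusion that was seen could still be reported as an AE.
- **Later correction.** It would be too strong to say the tallies could never be repaired. Onset date, description and the echo data would allow partial reconstruction. That is less reliable than recording the mode of detection at the time.
- **Removing scan-only events.** Treated thrombi may never become clinical, so dropping them could hide real maze harm. This stands fully and shapes the fix.

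**Conclusion.** The point holds for descriptive AE and SAE comparisons by arm. Ascertainment is unequal by design and, if true rates are equal, it works against the maze. The size cannot be derived from the documents. The range of 1.5 to 6 of 30 against 0 rests on assumed true rates of 5% to 20% and on detection by the study scan alone. At 80% versus 10% detection it falls to 1.2 vs 0.15 up to 4.8 vs 0.6.

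A reader might also infer that the asymmetry will stop the study. The text does not go that far: termination is discretionary and turns on SAEs that exceed expectation and are thought maze-related, not on a count by arm. Whether a silent thrombus in place counts as a thromboembolic event for the FDA report is likewise not stated. The realistic risk is a misread harm table, or one or two scan-only events weighed without noting that controls were not scanned. This is worth correcting before enrolment because the correction must be prospective and costs almost nothing.

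**What to change.** Leave the imaging schedule as it is: keep the maze-arm scan and add none in controls.

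1. Add one field to the REDCap AE form: *first detected by: symptoms or standard-of-care test / study pre-discharge echo only*.
2. State in the analysis text that the AE/SAE table by arm will be shown twice, side by side: once for events detected by means common to both arms, and once for all events.
3. List study-echo-only findings separately for the maze arm, with the number of patients imaged as denominator.
4. Continue to send every event to the safety reviewer and, where reportable, to the FDA. Flag scan-only events as having no control-arm counterpart, and do not remove them from any count.

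The cost is one data field and a few sentences, with no new procedures or patients. The downside is that events found and treated because of the scan may never become clinical, so the common-detection table may understate maze harm. The all-events table errs the other way when true rates are equal, which is why both are needed.

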- 7. Subjects currently on antiarrhythmic drugs Class I and III including amiodarone.

Study endpoints

The incidence or absence of documented AF, defined by Society of Thoracic Surgeons (STS) registry data as the occurrence of POAF or atrial flutter that requires treatment, is the primary endpoint (21). In addition, length of stay (LOS) and additional antiarrhythmic or anticoagulant medications will be examined as a secondary endpoint.

Safety endpoints

The safety endpoint is the occurrence of one of the following events between time of procedure and the 30 day post procedure assessment:

- All-cause death
- TIA/stroke
- Bleeding (chest tube drainage) that is procedure related and requires take back to the operating room or blood transfusions
- Incidence of AF
- Need for permanent pacemaker
- Evidence of pulmonary vein stenosis defined as > 50 % occlusion of the vessel.

Procedures Involved in the Research

Baseline preoperative cardiac surgery workup will be done on all patients according to standard of care. This workup will consist of:

- History and physical exam
- Chest X-Ray

- Electrocardiogram
- Echocardiogram
- Cardiac catheterization
- Blood and urine tests such as complete blood count, complete metabolic count, cardiac enzymes, type and screen, and urinalysis. Any other indicated tests based on patient history and index procedure i.e.; pulmonary function tests, carotid ultrasound, leg vein mapping, noncontrast chest CT.

Prior to enrollment, the protocol and informed consent must be approved by the Spectrum Health Institutional Review Board (IRB). IRB approved Health Insurance Portability and Accountability Act (HIPPA) will also be used. A regulatory binder and subject binders will be created according to local requirements and stored in the CV Research Department.

Before the subject signs the informed consent form (ICF), the investigator or designated study personnel will explain the research, study procedure, anticipated benefits, and potential risks of study participation. Adequate time will be allowed to read the ICF and ask questions. The original signed ICF will be kept with the subject's research records and a copy will be given to the subject.

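### Only the maze arm has a study echo that can trigger anticoagulation, yet the secondary endpoint counts new anticoagulants whatever their indication

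*Combined protocol and SAP*

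**What the plan says.** All references are to the combined protocol and SAP.

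- **The echo.** Under Procedures Involved in the Research, beyond standard care, "subjects who were randomized to the treatment arm of the study will have a pre-discharge transthoracic echocardiogram". The scan looks for left atrial thrombus, and the plan then sets the consequence of a positive finding: "If thrombi are noted, subjects will be anticoagulated per standard of care". The data list and the assessment schedule under Data management also confine this scan to the treatment arm, as does Cost to Subjects: "The pre-discharge transthoracic echocardiogram required for the study (treatment arm only) will not be billed".
- **Other routes to anticoagulation.** The same section starts anticoagulation for POAF that lasts beyond 24 hours or recurs. By valve type, "all patients who receive a mechanical valve or a bio prosthetic mitral valve are started on an anticoagulant on postoperative day 2". Patients in sinus rhythm after isolated pulmonary vein isolation get daily aspirin but are not routinely anticoagulated. All cardiac surgical patients receive daily Lovenox as prophylaxis.
- **The endpoint.** Study endpoints: "length of stay (LOS) and additional antiarrhythmic or anticoagulant medications will be examined as a secondary endpoint". No indication is specified.
- **The data.** Data management collects "Medications, pre- and post-op including name of medication, indication, dose". The list for the 6-week, 6-month and 12-month reviews asks for current and new medications without mentioning indication.
- **The analysis.** Statistical Methods has no rule for indication or for treatment started because of the study echo. It sets significance at 0.10. Chi-square or Fisher is named for POAF; no test is named for the medication endpoint.

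**The concern.** Background and Risks/Benefits to Subjects present extra anticoagulants as a burden of POAF that the maze procedure should remove. The secondary endpoint is the natural place to show that. As written, it also counts anticoagulation started because a scan done in one arm only showed thrombus. A control with the same silent thrombus has no study scan, and the standard postoperative care described includes no routine echo, so that thrombus would be found only if an echo were ordered clinically.

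Detection, and the treatment that follows it, therefore differ by arm for a reason unconnected with rhythm. On the anticoagulant endpoint the bias runs against maze. On TIA/stroke it could run the other way, because silent thrombus would be treated in one arm only. The trial is unblinded, so a decision taken after the results about which starts count would be open to the charge of being driven by the data.

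**Working it through.** The plan gives no figure to reproduce: there is no sample size calculation and no expected thrombus rate. The counts and rates marked as assumed below are for scale only.

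**Inputs from the documents.** 30 per arm (Sample Size Determination); level 0.10, sidedness not stated, two-sided assumed (Statistical Methods); baseline POAF risk of at least 40% (Study Design); a 21% POAF reduction in a cited study of prophylactic isolation during CABG, not stated to be relative or in points (Risks/Benefits to Subjects).

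**Step 1: weight of one start.** 1/30 = 3.3 percentage points, if the patient is not already anticoagulated for POAF or a valve.

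**Step 2: chance of any start.** For an assumed detected-thrombus rate t, the expected number is 30t and P(at least one) = 1 − (1 − t)^30.

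| t (assumed) | Expected | P(at least one) |
|---|---|---|
| 0% | 0 | 0% |
| 1% | 0.3 | 26% |
| 2% | 0.6 | 45% |
| 5% | 1.5 | 79% |
| 10% | 3.0 | 96% |

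**Step 3: effect on a test result.** Assume AF-driven anticoagulation in 8/30 controls and 2/30 maze subjects, then add echo-triggered starts to the maze arm. Uncorrected chi-square = 60(ad − bc)² / (30 × 30 × total anticoagulated × total not anticoagulated). For 8 vs 2: 60 × (8×28 − 22×2)² / (900 × 10 × 50) = 4.32.

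| Control vs maze | Chi-square | Chi-square p | Fisher p | Smallest expected count |
|---|---|---|---|---|
| 8 vs 2 (no start) | 4.32 | 0.038 | 0.080 | 5.0 |
| 8 vs 3 (one) | 2.78 | 0.095 | 0.181 | 5.5 |
| 8 vs 4 (two) | 1.67 | 0.197 | 0.333 | 6.0 |

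Under Fisher, one start crosses 0.10. Under uncorrected chi-square it takes two.

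**Step 4: effect on the estimated difference.** If a proportion p of the maze arm is anticoagulated for POAF, the observed proportion is p + (1 − p)t.

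- 21% read as points, every POAF case assumed anticoagulated: control 40%, maze 19%, difference 21.0 points. At t = 2%, maze is 0.19 + 0.81×0.02 = 20.6% and the difference 19.4 points; at 5%, 17.0; at 10%, 12.9.
- 21% read as relative, half of POAF cases assumed anticoagulated: control 20%, maze 15.8%, difference 4.2 points. At t = 5%, maze is 0.158 + 0.842×0.05 = 20.0%, and the difference disappears.

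**Step 5: other endpoints.** The POAF definition does not involve anticoagulation, so the primary endpoint is untouched. TIA/stroke is a safety component with no restriction on cause, so an effect is possible; the documents give nothing to size it. The bleeding component is confined to procedure-related chest tube drainage needing reoperation or transfusion, and anticoagulation begun after a pre-discharge scan has little route into that.

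**The case against.** The strongest reply is that the event may never happen. The protocol says epicardial pulmonary vein lesions of this kind are not known to have produced endocardial thrombus, with none reported for this clamp. Background places 90% of AF thrombi in the appendage, which the scanned arm has had removed. At an assumed 1% rate, the chance of no event in 30 is 74%. This stands: a reader might infer that the arms will differ, but the documents establish only that they can.

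A reader might also infer that a single start overturns the result. That holds under Fisher with these assumed counts. The smallest expected counts are 5.0 or more, which by the usual convention (an assumption, since the plan does not state its condition) would select chi-square, and then one start leaves p at 0.095. The example also lies near the boundary: going from 12 vs 3 to 12 vs 5 still gives Fisher p = 0.084 and chi-square p = 0.045.

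The valve rule is tempting as further evidence of bias. It applies to both arms under 1:1 randomisation, so it adds noise only.

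Part of the problem is already covered. Indication is recorded, and the Adverse events section requires the individual anticoagulation protocol and the numbers by arm to be reported for any thromboembolic event. Background and Risks/Benefits to Subjects use additional medication to mean drugs given because of POAF, so the endpoint could be read that way. But recording an indication is not a rule for using it, and the endpoint text does not state that restriction.

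Finally, thrombus after ablation and amputation may be a true effect of the procedure, and anticoagulation for it a real cost. Excluding it could flatter maze, and the indication is recorded by unblinded staff. This also stands, and it shapes the fix.

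**Conclusion.** The point holds for the anticoagulant endpoint. The plan counts, against maze only, anticoagulation triggered by a study scan that controls do not have. Each such start in a patient not otherwise anticoagulated is worth 3.3 percentage points. The number of starts is unknown and may be zero; one or two could change the reading at the 0.10 level, depending on the test and on the underlying counts, which are assumed here.

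The documents do not support a wider claim. The primary endpoint is unaffected, an effect on TIA/stroke is plausible but unquantified, an effect on the narrowly defined bleeding component is unlikely, and valve-related starts bias neither arm. This is a correctable gap in one secondary endpoint of a feasibility study. It is worth closing before results are seen.

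**What to change.** Leave imaging and treatment as they are, and change the wording of Study endpoints and Statistical Methods:

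1. Prespecify that new anticoagulant use is compared between arms for AF/flutter as the recorded indication.
2. Report total new anticoagulant use beside it, at equal standing, with a breakdown by arm into AF/flutter, echo-detected thrombus, valve and other.
3. State that thrombus found on the treatment-arm-only echo is a single-arm safety finding and is not compared between arms.
4. When TIA/stroke is reported, identify any subject anticoagulated because of that echo.

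The cost is mainly wording, because indication is already collected for pre- and postoperative medications. The sponsor should confirm that it is also captured at the follow-up reviews. The downside is reliance on an indication recorded by unblinded staff, together with the possibility that echo-triggered anticoagulation is a genuine cost of the procedure. For both reasons total use must stay visible and must not be demoted to a footnote.
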